6.10 LOSS TO FOLLOW-UP

Follow-up is only for 28 days, and therefore we anticipate a low rate of lost-to-follow-up. We plan to telephone parents/carers after 1, 2 and 3 weeks post-randomisation (when this occurs post-discharge) to ensure that contact is maintained before the face-to-face follow-up at week 4. The patient information sheets will be clear that maintaining contact for 28 days is a necessary part of inclusion in the trial, and parents/carers will be compensated for travel to the follow-up visit in accordance with existing recommendations by local ethics committees.

For operational management at participating sites, a child will be classified as “lost-to-follow-up” (meaning no further attempts at contact are made) only when three unsuccessful attempts have been made to contact the parent/carer following non-attendance at the face-to-face follow-up in week 4, including telephone calls in the first instance, and then attempts to visit a child’s home (based on the location provided at baseline). If a child is contacted after being classified as “lost-to-follow-up”, the 28-day follow-up form should be completed, regardless of the length of time it takes to re-establish contact with the family, in order to record the child’s vital status at the time of the missed week 4 follow-up.

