9.2 OUTCOME MEASURES

9.2.1 PRIMARY OUTCOME MEASURE

The primary outcome measure is:

- re-admission to hospital or death within 28 days post-randomisation (all-cause)

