9.5 ANALYSIS PLAN (BRIEF)

The analyses will be described in detail in a full Statistical Analysis Plan. This section briefly summarises the main issues.

The primary analysis population is intention-to-treat, including all randomised children, regardless of treatment received. This corresponds to estimating the impact of the effectiveness of the strategies of stepping down to oral amoxicillin vs co-amoxiclav and varying total duration of antibiotics. However, in secondary analyses we will also use inverse-probability weighting methods to adjust for deviation from randomised strategy, both duration of antibiotic treatment and oral-stepdown, which is a more efficient approach than defining a per-protocol population [55].

As follow-up is short (28 days post-randomisation) lost-to-follow-up should be low, and in each population, the primary comparison between randomised groups will be conducted using binomial regression, reported on the risk difference scale (following the sample size calculation which is based on risk differences). The primary analysis will adjust for the randomisation stratification factors (site and the other factorial randomisation). The primary analysis will be conducted on observed data. Secondary analyses will use multiple imputation with chained estimating equations to impute outcomes for the small (5%) number of expected missing outcomes due to losses to follow-up before 28 days post-randomisation (the sample size calculation in [Section 9.3](#) includes an inflation factor to allow for this). Imputation will be done separately within each randomised group to allow for unknown interactions, and will be based on outcomes and main baseline characteristics as recommended. Duration-response curves will be estimated separately for oral amoxicillin and oral co-amoxiclav randomised groups using fractional polynomials to flexibly model the impact of duration on response following Quartagno et al [33]. A combined model will test whether there is evidence that these duration-response curves vary between co-amoxiclav and amoxicillin using main effects and interactions (i.e. subgroup effects), specifically the following key factors:

- site

- severity
- age
- HIV infection and exposure
- malnutrition (assessed by weight-for-height Z-scores, according to the WHO Growth Standards, and pedal oedema/MUAC)

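### The observed-data primary analysis keeps children with an event before loss and drops those last known event-free, so each arm's 28-day failure risk is slightly overstated if loss is unrelated to prognosis

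*Protocol*

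**What the plan says.** The primary outcome (section 9.2.1) is all-cause readmission or death by day 28, counted from randomisation. Section 9.5 fixes the main elements of its analysis:

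- Population: "The primary analysis population is intention-to-treat, including all randomised children, regardless of treatment received".
- Model: "binomial regression, reported on the risk difference scale", adjusted for site and the other factorial randomisation.
- Data: "The primary analysis will be conducted on observed data".
- Missing data: as a secondary analysis, multiple imputation within each randomised group is used to "impute outcomes for the small (5%) number of expected missing outcomes due to losses to follow-up before 28 days post-randomisation". The imputation "will be based on outcomes and main baseline characteristics as recommended".

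Information before day 28 is collected. Section 6.10 says: "We plan to telephone parents/carers after 1, 2 and 3 weeks post-randomisation". Under section 6.6, readmission and death are asked about at the follow-up visits and calls, and both are also reportable as serious adverse events. Section 9.3.1 assumes 5% loss by day 28 and failure rates of 15% (amoxicillin) and 9% (co-amoxiclav).

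**The concern.** Section 9.5 treats loss before day 28 as a missing outcome. For this endpoint, however, an outcome becomes known as soon as an event occurs, while a non-event is known only at day 28. Among children who leave early, those who have already failed are therefore counted and those who have not are removed. Whether an outcome counts as observed depends partly on the outcome itself, even when loss has nothing to do with prognosis. Up to three weeks of confirmed event-free follow-up is discarded, and the analysed set falls short of all randomised children.

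Within an arm the failure risk is pushed upwards. Between arms the effect depends on whether loss is balanced. The trial is open-label and one arm stays on intravenous treatment for five days, so unequal loss is possible. In that case the risk difference can move in either direction.

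**Working it through.** **Inputs from the protocol.** Failure 15% v 9%, 500 children per oral arm, 5% loss, two-sided alpha 0.05 (section 9.3.1). The timing of events and losses, and any difference in loss between arms, are not given; those below are assumptions.

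**The plan's own figure.** With 475 per arm after 5% loss, the unpooled standard error is √[(0.15×0.85 + 0.09×0.91)/475] = 0.0210. Then 0.06/0.0210 − 1.96 ≈ 0.90, which gives 81.5% power (81.3% with pooled variance). The stated figure of more than 80% is reproduced.

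**Bias formula.** Let p be the true 28-day risk, L the proportion lost independently of outcome, and f the share of lost children's events that occur before loss. The risk among children with an observed outcome is

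observed risk = [p(1−L) + Lpf] / [(1−L) + Lpf].

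At f = 0 this equals p, so there is no bias if all loss precedes all events.

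**Worked case, L = 5% in both arms, f = 0.9.**
- 15%: (0.1425 + 0.00675)/(0.95 + 0.00675) = 0.1560
- 9%: (0.0855 + 0.00405)/(0.95 + 0.00405) = 0.0939
- Difference: 6.2 points instead of 6.0

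At f = 0.5 the values are 15.3%, 9.2% and 6.1 points.

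**Range over timing patterns.** Events were spread evenly or weighted early. Losses were spread evenly, placed on days 4-8, or placed on days 21-28. At 5% loss in both arms, 15% becomes 15.1-15.7%, 9% becomes 9.1-9.4%, and the difference is 6.05-6.23 points. The upper limit, if no lost child would have had a later event, is 15/0.95 = 15.8% and 9/0.95 = 9.5%.

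**Equal loss under the null.** With the same p, L and f in both arms, the two observed risks are identical and the difference is zero.

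**Unequal loss (assumed splits).**

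| Situation | Loss | Result |
|---|---|---|
| Null at 12%, f = 0.9 | 7% v 3% | 12.71% v 12.29%: 0.42 points |
| Null at 12%, f = 0.5 | 7% v 3% | 12.40% v 12.16%: 0.23 points |
| 15% v 9%, f = 0.9 | amoxicillin 7%, co-amoxiclav 3% | difference 6.6 points |
| 15% v 9%, f = 0.9 | amoxicillin 3%, co-amoxiclav 7% | difference 5.8 points |
| Null at 12%, timing patterns above | 2% v 8% | 0.15-0.68 points |

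The standard error at 475 per arm is 2.1 points. At a 12% null, a bias of 0.5 points would raise the two-sided error from 5% to about 5.6%, so 0.2-0.4 points does less than that.

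**Imputation, if event-free time were left out.** With p = 15% and f = 0.9, a child known event-free at last contact has remaining risk p(1−f)/(1−pf) = 0.015/0.865 = 1.7%. Imputation within arm from baseline covariates alone would assign about 15.6%. On average it would return the observed-data estimate.

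**Precision.** Retaining partial follow-up moves power from 81.5% (475 per arm) towards 83.4% (500 per arm). The second figure is a ceiling.

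**The case against.** **The imputation half goes too far.** A reader might infer that the imputation ignores the weekly contacts and so must share the bias of the primary analysis. The protocol does not say that. It names outcomes and main baseline characteristics as predictors without defining outcomes, which could include weekly status, and it leaves detail to a statistical analysis plan that is not at hand. This objection stands: the shared bias is conditional, and all that can be said is that the protocol does not state whether event-free time is used.

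**The direction is not certain.** If children lost after their last contact die or are readmitted more often than the others, the observed risk may be too low. This also stands. Overstatement holds for loss unrelated to prognosis, and censoring at last contact relies on the same kind of assumption.

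**Tracing will leave few outcomes missing.** Section 6.10 counts a child as lost only after three failed attempts following a missed week 4 visit, including attempts to visit the home, and asks for the 28-day form whenever contact is regained. Section 6.1 allows week 4 by telephone, and section 6.1.3 has two numbers tested before discharge. This stands in part. The stated aim of the late form and of the tracing in section 9.2.4 is vital status, which does not settle whether the child was readmitted.

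**The effect is small and no conclusion is shown to change.** This is correct for the comparison. At 5% equal loss the shift is about a tenth of a standard error, and the unequal splits are assumed.

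**The binomial model was chosen to match the sample size calculation.** That is a reason to keep the risk-difference scale. A censored analysis can report the same quantity.

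**Conclusion.** The concern holds as a matter of analysis choice. Section 9.5 fixes a method that retains early failures and discards confirmed event-free time, although the data for a better estimate are collected.

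If loss is unrelated to prognosis, each arm's risk is overstated by about 0.1-0.7 points at 5% loss. The risk difference moves by under 0.25 points with equal loss and is unbiased under the null. With an assumed 7% v 3% loss, a true null at 12% shows about 0.2-0.4 points. Successful tracing would reduce all of these.

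The result rests on reading an event before loss as an observed outcome, which is the natural reading of an intention-to-treat analysis on observed data, and on the assumed timings and loss splits. It should not be read as showing that the power statement is wrong, that type I error is materially inflated at the planned loss, or that failure is certain to be overstated. The stated power of more than 80% already allows for 5% loss and is reproduced.

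**What to change.** In section 9.5, or in the statistical analysis plan:

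1. Estimate each arm's 28-day risk from time to first readmission or death, censoring children without an event at the last contact at which they were known to be event-free. Adjust for site and the other factorial randomisation, for example with a weekly discrete-time model standardised to day 28, and report the 28-day risk difference. The estimand and scale are unchanged.
2. State that the multiple imputation conditions on event-free time to last contact and imputes only the remaining interval.
3. Keep a sensitivity analysis for informative loss, because the censored analysis still assumes that loss after last contact is non-informative.

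No new data are needed: the weekly contacts and serious adverse event reports already supply event and contact information. The cost is extra analysis work, including carrying the same handling into the fractional-polynomial duration-response model and its interaction tests. It is best settled before outcomes by arm are seen.

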X[†] indicates that oral step-down antibiotics will be prescribed to complete the randomised total duration of antibiotic therapy at the point the child can tolerate oral medication

(X) indicates tests that may be done if the child's condition requires it or allows it and is local standard of care, but these investigations are not mandatory and are not paid for by the trial. Results will be collected, if available.

Note: Week 4 visit may be conducted by telephone if child is unable to come to clinic. For any child in hospital on day 28, the total duration of that hospitalisation and resource use during it will be collected through to discharge.

Additional explanatory notes for investigations

^a Nurse administered questionnaire at discharge and telephone follow-up.

^b Includes sociodemographic and socioeconomic information, mode of delivery, documentation of immunisation status (including taking copies of immunisation records where available (copies will be taken at week 4 if not brought at the original admission)), documentation of any underlying diseases, duration of symptoms to date, recent antibiotic exposure, height/length and upper middle arm circumference. Height/length and upper middle arm circumference may be collected post-baseline if not possible to assess at trial entry.

^c Includes vital parameters (respiratory and heart rate and oxygen saturation) and temperature.

^d If clinically reviewed by the trial team.

^e Includes documentation of relevant physical signs and symptoms, as well as specific solicited side-effects and adverse events post-randomisation.

^f For example administration of parenteral fluids and antibiotics, intensive care transfers and discharge from hospital as well as re-hospitalisation during the follow-up period, and further antibiotic treatment post-discharge; for outpatients elicited during phone follow-up.

^g Semi-quantitative point-of-care test using finger or heel prick only, or venous blood taken as part of routine care.

^h If available (performed locally following standard of care; not to be done specifically for research), haemoglobin, platelet count, leukocyte count, neutrophil count, white cell count, eosinophil count.

ⁱ If available (performed locally following standard of care; not to be done specifically for research), C-reactive protein, procalcitonin, urea, creatinine and electrolytes.

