3.1 CHILD INCLUSION CRITERIA

1. Aged 2 months to 6 years inclusive
2. Weighing ≥ 3 kg and <30 kg
3. Admitted to hospital with severe pneumonia judged to require at least 24h of intravenous antibiotics by the treating physician
4. Difficulty breathing (with or without cough reported by parent/carer) PLUS one or more of
 - a. Central cyanosis or hypoxaemia (room air pulse oximetry $<90\%$)
 - b. Any sign of severe respiratory distress (e.g. severe chest indrawing, grunting, nasal flaring, head nodding)
 - c. Signs of pneumonia (fast breathing (defined as respiratory rate ≥ 50 breaths per minute at age 2-11 months and ≥ 40 breaths per minute at age 1 years or older) or chest indrawing) PLUS a general danger sign (inability to breastfeed or drink, lethargy or reduced level of consciousness, convulsions, moderate/severe malnutrition)occurring at any time from admission up to randomisation.
5. About to initiate or already initiated intravenous benzylpenicillin plus gentamicin, ampicillin plus gentamicin, benzylpenicillin or ampicillin alone, ceftriaxone alone or cefotaxime alone
6. Received at most 24h of these intravenous antibiotics at the point of randomisation (that is, first dose of any intravenous antibiotics must have been administered no more than 24h previously at randomisation)
7. Parent/carer willing to accept and adhere to all possible randomised allocations for their child (including 5 days of intravenous antibiotics if joining PediCAP-A) and signed written informed consent available from parent/carer
8. Available for follow-up for the entire study period; specifically, parent/carer willing to return with their child to clinic at 4 weeks, and be contacted at minimum by telephone at weeks 1, 2 and 3

For children enrolled in PK ([Section 10.1](#)) or microbiology ([Section 10.2](#)) substudies, additional inclusion criteria are:

9. If undergoing additional PK sampling: willing to provide samples and potentially to stay in hospital for up to an additional 12h (separate consent will be obtained for PK sampling which may be refused and the child still join the main trial (PediCAP-A): consent for PK sampling is required for inclusion in the Phase II PK trial (PediCAP-B))

10. If undergoing additional microbiological sampling: willing to provide samples at enrolment, discharge and week 4 (separate consent will be obtained for microbiological sampling which may be refused and the child still join the main trial (PediCAP-A))

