3.5 SCREENING PROCEDURES & PRE-RANDOMISATION INVESTIGATIONS

Potentially eligible children for PediCAP-A and PediCAP-B will be identified prior to completing 24h of intravenous antibiotics, ideally at the time intravenous antibiotics are initiated. Parents/carers of potentially eligible children based on clinical inclusion and exclusion criteria will be given a short information leaflet on the trial. If interested, they will then be given a concise information sheet relating to screening for the PediCAP trial and will be asked to give written consent before trial-specific point-of-care CRP testing (using an additional finger or heel prick or as part of a routine care blood draw). Parents/carers of eligible children (requiring CRP >10mg/l) will then be given an information sheet about the full PediCAP trial and asked to give written consent before any further trial-specific procedures, including randomisation, are performed or any further samples are taken for the trial. Separate information sheets will be used for PediCAP-A and PediCAP-B because PediCAP-B does not include a randomisation to total duration of antibiotic therapy and because all children in PediCAP-B undergo PK sampling and consent must be provided for this. Each child will be

approached for recruitment into either PediCAP-A or PediCAP-B (not both and not sequentially). Signed consent forms (screening and trial entry) must be kept by the investigator and documented in the case record form (CRF)\worksheet and a copy given to the child or family.

It will be made completely and unambiguously clear that the child and/or parent/carer of the child is free to refuse to participate in all or any aspect of the trial, at any time and for any reason, without incurring any penalty or affecting the child's treatment. See [Section 0](#) for more details on procedures around child withdrawal from the trial.

Eligible children should be randomised as soon as possible and prior to completing 24 hours of intravenous antibiotics (that is, the first dose of any intravenous antibiotics must have been administered no more than 24h previously at the point of randomisation). Confirmation of eligibility criteria and written informed consent must be obtained before randomisation.

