5.4 INADEQUATE RESPONSE TO TREATMENT

The management of potential inadequate response to intravenous antibiotics or the randomised antibiotic regimen and/or relapse after the completion of therapy as prescribed will be based on a

range of potential scenarios. These will be fully described in the MOP, but example scenarios are included in **Table 8** below.

Table 8: Example scenarios of inadequate response or relapse

TIMING	SCENARIO	ACTION*
DURING PRIMARY HOSPITAL ADMISSION OR WITHIN ORIGINALLY RANDOMISED TREATMENT COURSE		
Any time	Child clinically deteriorates, e.g. with severe respiratory distress or septic shock	Chest X-ray is strongly recommended. Treat with injectable antibiotics as per normal standards of care (e.g. moving to second line treatment regimen according to local standard of care).
	Positive blood culture or other test result suggesting more serious manifestation of severe CAP	Manage according to local standard of care (e.g. moving to different intravenous antibiotics, treating for longer than original randomisation depending on clinical status of the child).
After two days IV	No improvement in clinical status on IV therapy	Manage according to local standard of care (e.g. moving to cloxacillin if staphylococcal pneumonia is suspected, or to second-line, or repeating laboratory tests where available). Consider TB.
After oral switch	Child has persistent symptoms and signs of a respiratory tract infection after oral switch, e.g. with continued fever, tachypnoea, tachycardia, but remains clinically stable. Appears to be tolerating oral medication.	Continue oral medication as randomised: most likely infection is viral. Also consider evaluation for TB.
	Child has persistent symptoms and signs of a respiratory tract infection and is NOT tolerating oral medication due to severe persistent vomiting or diarrhoea	Switch to IV or injectable antibiotics as per normal standards of care.
AFTER DISCHARGE FROM PRIMARY ADMISSION OR AFTER COMPLETION OF INITIAL RANDOMISED COURSE		
Any time	Child has persistent symptoms of a mild respiratory tract infection, with no signs of pneumonia	No treatment for CAP. A child with persistent cough and fever for more than 2 weeks and signs of pneumonia after adequate antibiotic treatment should be evaluated for TB.
	Child has signs of pneumonia, and fulfils the diagnostic criteria of non-severe CAP	Treat as per normal standards of care. Consider TB.

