6.1.1 BASELINE INFORMATION

At randomisation, medical and relevant social history, including demographics and socioeconomics, documentation of any underlying diseases, mode of delivery, documentation of immunisation status (including taking copies of immunisation records where available), duration of symptoms to date and recent antibiotic exposure, will be recorded. Locator information, including physical address and contact phone numbers will also be collected. Anthropometry will include weight, height/length and mid-upper arm circumference (MUAC) (height/length and MUAC may be collected as soon as practicable post-baseline if not possible to assess at trial entry). Vital signs (respiratory and heart rate, oxygen saturation) and temperature will be measured. Relevant respiratory symptoms and signs will be solicited. Chest X-rays at randomisation will be strongly encouraged where site facilities allow, but are not mandatory. Where possible, and where available, digital copies of all chest X-ray images will be collected.

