- initial IV regimen (benzylpenicillin plus gentamicin or ampicillin plus gentamicin, vs benzylpenicillin or ampicillin alone, vs ceftriaxone alone or cefotaxime alone)
- prior oral/intramuscular antibiotics before hospitalisation for the index CAP episode
- baseline CRP (semi-quantitative, 10-40 vs 40-80 vs >80 mg/l)
- chest X-ray features (abnormal vs normal vs uninterpretable vs not done based on any chest X-ray up to and including 72h from admission).

Secondary outcome analyses will similarly use exact tests and binomial regression for binary outcomes, and t-tests and normal linear regression (potentially on transformed data depending on the observed data distribution, adjusted for baseline values) for continuous outcomes. Ranksum tests will be used if there is gross departure from normality that cannot be adequately addressed by data transformation. Adverse events will be summarised by body system.

A Statistical Analysis Plan will be written and approved by the Trial Management Group (TMG), Trial Steering Committee (TSC) and the DMC before the first interim analysis is reviewed by the DMC.

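### The chest X-ray subgroup factor accepts films up to 72h from admission, so category membership can depend on what happens after randomisation

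*Protocol*

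**What the plan says.** Section 9.5 of the protocol names the factors to be examined for subgroup effects, through main effects and interactions, in the combined model of the amoxicillin and co-amoxiclav duration-response curves. The last factor is chest X-ray features, classed as "abnormal vs normal vs uninterpretable vs not done based on any chest X-ray up to and including 72h from admission". The window is anchored to admission, and nothing limits it to films taken before randomisation.

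Four other parts of the protocol bear on this.

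- **Timing of randomisation.** Section 3.1 requires that the "first dose of any intravenous antibiotics must have been administered no more than 24h previously at randomisation". Section 3.5 adds: "Eligible children should be randomised as soon as possible and prior to completing 24 hours of intravenous antibiotics".
- **Start of randomised oral treatment.** Section 5.2.1 allows step-down once at least 24h of intravenous treatment has been given.
- **Who is filmed.** Section 6.1.1 says: "Chest X-rays at randomisation will be strongly encouraged where site facilities allow, but are not mandatory". Table 1 lists the film as conditional at randomisation, daily until discharge and at any acute event. Its notes explain that such tests may be done if the child's "condition requires it or allows it and is local standard of care, but these investigations are not mandatory".
- **Deterioration.** For a child who worsens at any time in the primary admission or the randomised course, Table 8 in Section 5.4 states: "Chest X-ray is strongly recommended".

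Treatment is open-label (Section 5.1).

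**The concern.** A subgroup analysis asks whether the treatment effect differs by a characteristic that allocation cannot have changed. A film taken after randomisation does not guarantee that, and here the reason for taking it may be the child's response. A child without an entry film who worsens on day 2 or 3 is likely to be filmed and may be read as abnormal; the same child doing well stays in 'not done'. If early worsening is more frequent on one drug, more of that arm's high-risk children move category, and the stratum-specific risk differences shift even when the true effect is the same everywhere. Staff who know the allocation may also order films differently by arm.

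Objective 3 in Section 1.5 asks whether antibiotic selection or duration should be tailored to subgroups, so a false interaction, or a masked one, could influence that discussion.

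**Working it through.** **1. The window.** Assume the first intravenous dose is given at admission (the protocol gives no interval). With randomisation t hours after admission, the post-randomisation part of the window is 72 − t:

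| t (h) | Post-randomisation window (h) |
|---|---|
| 0 | 72 |
| 6 | 66 |
| 12 | 60 |
| 24 | 48 |

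Step-down is possible from 24h, so up to 72 − 24 = 48h can overlap randomised oral treatment. If the first dose comes L hours after admission, this overlap falls to 48 − L.

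**2. Which contrasts are exposed.** Drug can differ between arms from 24h of intravenous treatment. Duration cannot differ in treatment received until the shortest course ends, at 4 × 24 = 96h, which is beyond 72h.

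**3. Other factors in the list.** The CRP factor is labelled baseline. Initial intravenous regimen and prior antibiotics are fixed before randomisation. The X-ray factor has an explicit window running past it.

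**4. Possible size: film versus not done.** The only figure on film use is 31/79 = 39.2% in Table 3, with no timing given. It is used here as an assumed share f with an entry film. The other inputs are also assumed: early deterioration d; probability q that an unfilmed deteriorating child is filmed; event risk r1 if deteriorated and r0 if not. For each arm:

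- total risk T = d·r1 + (1 − d)·r0
- share not done N = (1 − f)(1 − d·q)
- events in not done E = (1 − f)[d(1 − q)·r1 + (1 − d)·r0]
- risk in not done = E/N; risk in film = (T − E)/(1 − N)

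With q = 0.9, r1 = 0.40 and r0 = 0.12:

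| | d | T | Not done | Film |
|---|---|---|---|---|
| Amoxicillin | 0.10 | 14.8% | 0.0681/0.5529 = 12.3% | 0.0799/0.4471 = 17.9% |
| Co-amoxiclav | 0.05 | 13.4% | 0.0705/0.5803 = 12.1% | 0.0635/0.4197 = 15.1% |

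The true difference is −1.4 points in every baseline stratum. It appears as −0.2 in not done and −2.8 in film, a spurious interaction of −2.6 points from unrounded values. With q = 0.5, r1 = 0.30 and r0 = 0.13 the interaction is −0.9. With equal deterioration (10% in both arms) it is 0.

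**5. Possible size: abnormal versus not done.** Take the design risks of 15% and 9% in every stratum (Section 9.3.1). Assume 20% of children abnormal at entry and 61% unfilmed. Let 8% versus 4% of the unfilmed deteriorate, all of them filmed and read as abnormal, with 40% event risk.

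- Abnormal, amoxicillin: (0.20×0.15 + 0.61×0.08×0.40)/(0.20 + 0.0488) = 19.9%
- Abnormal, co-amoxiclav: (0.20×0.09 + 0.61×0.04×0.40)/(0.20 + 0.0244) = 12.4%; difference −7.5
- Not done: (0.15 − 0.08×0.40)/0.92 = 12.8% versus (0.09 − 0.04×0.40)/0.96 = 7.7%; difference −5.1

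The spurious interaction is −2.4 points. It is −0.8 with 6% versus 4%, about 0 with 5% versus 4%, and +0.9 with 4% versus 4%.

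**6. Against sampling error.** With 500 per arm, the standard error of the interaction is the square root of the sum of p(1 − p)/n over the four cells. In the 8% versus 4% case the cells hold about 124, 112, 281 and 293 children, giving √0.00289 = 5.4 points. The bias is 2.4/5.4 = 0.45 standard errors, and a nominal 5% test would reject about 7.3% of the time. In the −2.6 case of step 4 the standard error is √0.00203 = 4.5 points, the bias 0.58 standard errors and the rejection rate about 8.9%.

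**The case against.** The strongest reply is that little can go wrong in so short a time. No oral drug is given before 24h. Section 1.4.2 expects 1 to 3 days of intravenous treatment, so many children may be on common therapy for most of the 72h. Step-down requires clinical improvement. During the primary admission, Table 8 recommends a film only for clinical deterioration, not for failure to improve or for persistent symptoms in a stable child. The numerical cases that show a visible bias assume deterioration differing about twofold between drugs, which nothing in the protocol supports. The 39% is not a baseline figure, and encouragement of entry films may raise that share and shrink the group able to change category. A later film may also show changes not visible at entry. Finally, Section 9.5 is a summary, and the analysis plan might add a baseline-only analysis.

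Most of this stands as a limit on size. It does not remove the problem: the window is a rule the protocol states, and an unseen plan does not correct it. Enlarging the strata with films partly selected by deterioration justifies a sensitivity analysis, not the main definition.

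Stronger readings are tempting and unsupported. A reader might infer that the subgroup is certainly affected by treatment and outcome; the protocol shows only that it can be, mainly through early deterioration that predicts readmission or death. A reader might extend the bias to an oral-versus-intravenous interaction by X-ray status, but Section 9.5 specifies none. A reader might also think treatment duration itself alters the factor, but durations do not differ in treatment received before 96h.

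**Conclusion.** The point holds in limited form. As written, the X-ray factor can be determined after randomisation and can depend on allocation, through early clinical course or open-label ordering. The co-amoxiclav versus amoxicillin interaction with this factor is therefore not a clean baseline subgroup analysis. The duration contrast is exposed only through ordering of films.

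The size is unknown. Under assumed inputs the spurious interaction is about 0 to 2.6 points in absolute size, its sign is not fixed, and it is roughly half a standard error or less. The timing argument rests on intravenous treatment starting near admission. One of the nine listed factors is involved; the primary intention-to-treat comparisons and the sample size are untouched.

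**What to change.** In Section 9.5, define the factor from chest X-rays taken at or before randomisation, and class every other child as 'not done at baseline'. Keep the 72h definition only as a labelled sensitivity analysis, or report later films descriptively by arm.

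This changes wording only: no added procedure and no change to the sample size. It needs the date and time of each film to be comparable with the time of randomisation. The downside is that children first filmed after randomisation move to 'not done at baseline', so the film strata shrink by a number the protocol does not allow to be estimated.
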